2.3 RISK/BENEFIT ASSESSMENT

2.3.1 KNOWN POTENTIAL RISKS

Ulipristal acetate is a 30mg tablet progesterone receptor agonist/antagonist that was FDA approved for emergency contraception in 2010. Adverse events noted from an open-label multicenter trial and a randomized, single-blind multicenter trial include headache (18%), nausea (12%), and abdominal pain (12%). Other less common side effects include dysmenorrhea, fatigue and dizziness. Post marketing experience has also shown an increase in acne among users of the medication [16].

This study will be utilizing a dosage of UPA 90mg to most closely match the effects of mifepristone 200mg, which is the dosage studied for EPL based on a study of endometrial histology showing similar effects of UPA 100mg to mifepristone 200mg [2,19]. FDA approval indicated that experience with single dose equivalent of up to four times the standard UPA dose were administered to a limited number of subjects without any adverse reactions, suggesting that UPA 90mg may be used safely in this patient population [16]. In a pilot study of ulipristal acetate 90mg at the dose that would be used for this study, no significant adverse events were noted [23].

Additionally, there will be two blood draws required for the study to monitor liver function testing. Possible risks of these blood draws include mild risks of pain, bruising and fainting. These risks are infrequent, and all lab draws will be completed by clinic nurses or the study coordinator, who have been trained in phlebotomy.

Possible psychologic risks of the study include consequences of breach of confidentiality. All study materials will be kept solely with research staff. All medical care will be documented in the UNC EPIC system, which has safeguards to reduce the risk of confidentiality breaches.

Possible social risk includes the risk of stigmatization of UPA if used in the context of EPL. Just as mifepristone is known as the "abortion pill", making it less likely to be used in other settings, UPA may undergo similar stigmatization, which may change prescribing patterns of UPA.

Possible economic risks include loss of income and time for follow up appointments, as patients undergoing medication management of EPL generally are followed up with a phone call as opposed to an in-person appointment. Patients will be compensated for their travel time and will not have to pay for their follow up visits.

2.3.2 KNOWN POTENTIAL BENEFITS

There are no direct benefits to patients enrolling in this study. Participants will receive care for their EPL with appropriate follow up over the course of the study.

2.3.3 ASSESSMENT OF POTENTIAL RISKS AND BENEFITS

While there are no direct benefits of UPA to study participants, UPA is very well tolerated with minimal side effects or adverse events noted from FDA pre-marketing and post marketing analysis. Further, all participants will also get misoprostol, which in clinical environments that do not prescribe mifepristone, is the standard of care for medical management of EPL.

Societally, demonstration of feasibility of UPA for EPL may improve access to effective medical management for EPL. While mifepristone has been shown to increase effectiveness of medical management of EPL and decrease need for additional intervention for pregnancy expulsion, challenges with access to mifepristone limit its use. Thus, if UPA were to be a feasible alternative to mifepristone pretreatment, patients desiring medical management of EPL would have an effective option for treatment that can be more easily obtained.

3 OBJECTIVES AND OUTCOMES

OBJECTIVES	OUTCOMES	JUSTIFICATION FOR
		OUTCOMES
Primary		
To assess whether it is feasible to study UPA plus misoprostol as an intervention for medical management of EPL for larger future studies.	Recruitment: number of participants in study/number of patients screened for participation Adherence: number of participants adhering to study intervention (UPA + misoprostol vaginally after 6-18 hours)/number of participants in study Retention: number of participants	Study outcomes of interest for feasibility based on outcomes of interest appropriate for pilot studies [24-26].
	attending all study visits (day 0, 3/8, 30)/number of participants in study	
Secondary	30)/ Humber of participants in study	
Secondary		

OD LECTIVIES	OUTCON AEC	U (CT) 5 (CA T) CA L 5 C C
OBJECTIVES	OUTCOMES	JUSTIFICATION FOR
		OUTCOMES
To evaluate if participants taking UPA plus misoprostol achieve complete resolution of EPL.	Absence of gestational sac on transvaginal ultrasound examination on Day 3 follow up	Same outcome was used in randomized controlled trial of mifepristone plus misoprostol for early pregnancy loss to calculate effective intervention [2].
To investigate if UPA plus misoprostol is associated with side effects or adverse events when used for EPL.	Participants self-report of side effects or adverse events following UPA and misoprostol.	Study outcomes of interest for feasibility based on outcomes of interest appropriate for pilot studies [24-26].
To identify if UPA plus misoprostol is acceptable to patients for treatment for EPL.	Participants willing to use this combination of medication again for another early pregnancy loss or recommend this combination of medications to a friend.	

4 STUDY DESIGN

4.1 OVERALL DESIGN

This is a phase 2 single site pilot study of UPA for use in medical management of early pregnancy loss. Our hypothesis is that UPA will be a feasible option for women desiring medical management. Specifically, we estimate that over 60% of participants screened for participation will enroll in the study (based on a recruitment rate of 75% in a prior study of mifepristone plus misoprostol for EPL) [2]. Additionally, we estimate that greater than 50% of participants will be able to adhere to the study protocol in taking UPA and misoprostol at the designated times and greater than 90% of participants will be able to complete follow up for the study. This is a pilot study with a small sample size and thus our secondary aims will only be for hypothesis generating activities, not hypothesis testing activities.

The study will be conducted at UNC Chapel Hill. Patients will be approached as a convenience sample from patients diagnosed with EPL on viability scan at UNC Chapel Hill OBGYN clinics and UNC Chapel Hill Emergency Department between 5- and 12-weeks' gestation desiring medical management. Participants will be provided counseling regarding their EPL by their OBGYN physician and subsequently screened for eligibility by a research coordinator. Based on prior data on recruitment in this setting and number of patients seen desiring medical management for EPL at UNC Chapel Hill, we anticipate 40 women will be eligible for participation and desire participation in the study after recruitment for 12 months.

After providing informed consent, participants will complete a demographic questionnaire and ensure that they have appropriate baseline lab work (hemoglobin, ABO/Rh status, liver function testing). Participants will all receive the study intervention of 90mg UPA and will be instructed to self-administer 800mcg misoprostol vaginally 6 to 18 hours after the study drug is administered. Self-administration of misoprostol is the standard of care for medical management of EPL. As all participants will receive the same intervention, no randomization or blinding will take place. Participants will receive an

appointment card with their follow up appointment date that also provides space for participants to document their misoprostol timing at home.

Follow up of medical management of EPL generally consists of confirmation of pregnancy expulsion by ultrasound examination or serial beta-hCG measurements in settings where ultrasound is not available [1]. There is no standard of care regarding specific intervals when ultrasonography or laboratory follow up assessment should take place. Study follow up schema for our study is based on participant follow up design from a similar study of mifepristone and misoprostol for EPL [2].

Participants will follow up with the UNC Family Planning Division for a transvaginal ultrasound on study day 3 to ensure expulsion of the gestational sac. Women generally experience cramping and vaginal bleeding 1 to 4 hours following misoprostol administration and pass their pregnancy within 24 hours of starting to bleed. Thus, follow up on day 3 will assess participants who are able to pass their pregnancy with a single dose of UPA and misoprostol.

For those who still have a pregnancy in the uterus, they will be offered an additional dose of 800mcg misoprostol, expectant management, or surgical management. Those who did not have expulsion of the pregnancy on day 3 and elect for an additional dose of misoprostol or expectant management will follow up with the UNC Family Planning Division for another transvaginal ultrasound on study day 8 to ensure expulsion of the gestational sac. As some studies of EPL assess for response 7 days after medication administration, we will be able to compare our data to similar studies through our day 8 follow up results [3]. Further, twenty-five to thirty percent of EPL will pass with expectant management alone one week after diagnosis [27].

Participants will be assessed for possible liver toxicity on study day 14 through a laboratory test of ALT, AST and total bilirubin.

All study participants will receive a phone call on study day 30 to what additional treatment patients needed for their early pregnancy loss, investigate any side effects or adverse events, and identify acceptability of the treatment. Most symptoms of bleeding and abdominal cramping following medical management of EPL occur in the first two to four weeks following medication administration; thus, 30 days is an adequate time to assess for side effects and acceptability of treatment while not being too remote from the time of the pregnancy passing.

A detailed description of all study visits is provided below:

Visit 1 (Day 0):

- Participant is screened for eligibility by the study coordinator and offered admission to study if eligible
 - Review of radiologic imaging to confirm early pregnancy loss based on eligibility criteria
 - Review of physical exam findings and vital signs (heart rate, blood pressure, temperature) to ensure that patient is hemodynamically stable and not having an inevitable or incomplete abortion based on eligibility criteria
- Participant reviews and signs informed consent and HIPAA authorization form
- Participant completes paper baseline demographic questionnaire
- Participant will have hemoglobin, ABO/Rh status and liver function testing (ALT, AST, total bilirubin) if not already performed by primary OBGYN

 Participant takes 90mg ulipristal acetate with study team; given prescription for 800mcg misoprostol to take at home

Visit 2 (Day 3 ± 1 day):

- Participant returns to UNC Family Planning Clinic
- Participant has vital signs checked by RN at clinic
- Participant fills out questionnaire regarding bleeding symptoms and any side effects or adverse
 events after taking the ulipristal acetate and misoprostol, including reporting time and route of
 administration of misoprostol at home
- Participant has a transvaginal ultrasound completed by the principal investigator to ensure that the pregnancy has passed (no gestational sac visualized on ultrasound)
- If pregnancy is still in the uterus, patient will be offered surgical management, medical management (an additional dose of misoprostol 800mcg), or expectant management

Visit 3 (Day $8 \pm 1 \text{ day}$):

- Participant will only attend this visit if a gestational sac was still present on ultrasound on Visit
 2 and patient opted for medical management or expectant management. If gestational sac is absent at Visit 2, participant will not need Visit 3. All participants will complete Visit 4.
- Participant returns to UNC Family Planning Clinic
- Participant has vital signs checked by RN at clinic
- Participant fills out questionnaire regarding bleeding symptoms and any side effects or adverse events after taking the ulipristal acetate and misoprostol
- Participant has transvaginal ultrasound completed by the principal investigator to ensure that the pregnancy has passed (no gestational sac visualized on ultrasound)
- If pregnancy is still in the uterus, patient will be offered surgical management, medical management (if patient did not receive additional misoprostol at Visit 2), or expectant management
 - If patient has medical management or expectant management, patient will be followed with weekly transvaginal ultrasounds until pregnancy has passed. No study questionnaires will be administered at these visits. Patient may elect for surgical management at any follow up visit as per the standard of care.

Lab Visit (Day 14 ± 1 day):

 Participant will have liver function testing (ALT, AST, total bilirubin) performed at outpatient laboratory

Visit 4 (Day 30 ± 7 days):

Participant will be called by the principal investigator to administer a follow up questionnaire
about any additional treatments taken to help pass the pregnancy, any side effects experienced
with the medication and participant acceptability

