8 STUDY ASSESSMENTS AND PROCEDURES

8.1 FEASIBILITY ASSESSMENTS

At the time of recruitment to the study, participants' medical charts will be utilized to confirm the diagnosis of early pregnancy loss by ultrasound diagnosis. A HIPAA authorization form will be obtained from patients at the time of enrollment into the study, as EPL care will be documented in the UNC EPIC electronic medical record as well as in the study documentation. Any adverse events noted in the UNC EPIC electronic medical record during the study follow up time that are not associated with a study visit will be abstracted into the study documentation to appropriately follow up adverse events.

Once study participants have been approached, administration of UPA should occur within 14 days of diagnosis of early pregnancy loss, as over 50% of patients will have completion of their miscarriage with expectant management alone 14 days after diagnosis of early pregnancy loss [27]. Following administration of ulipristal acetate 90mg PO, participants will place misoprostol 800mcg vaginally 6 to 18 hours after ulipristal acetate. Study participants will note the time of misoprostol administration on their appointment card and report the time of misoprostol administration at their subsequent visit to ensure adherence to the study protocol.

Patients will return to clinic on day 3 for a transvaginal ultrasound to confirm absence of a gestational sac. Transvaginal ultrasound will be performed by an obstetrician/gynecologist (fellow or attending) in the UNC Family Planning Clinic to confirm absence of the gestational sac. These physicians have training in transvaginal ultrasound in early pregnancy. If participants are still noted to have a pregnancy in the uterus, they will be offered expectant management, medical management with an additional dose of 800mcg misoprostol, or surgical management with manual or electric uterine aspiration based on gestational age. Those patients with a pregnancy still in the uterus will return to clinic again on day 8 for an additional transvaginal ultrasound and again be offered options if pregnancy is still present. All patients will receive a phone call 30 days following misoprostol administration to assess for additional treatments needed, side effects, adverse events, and patient acceptability.

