8.2 SAFETY AND OTHER ASSESSMENTS

At the time of diagnosis of EPL, the research coordinator will utilize the medical chart to review ultrasound images to confirm the diagnosis. Research personnel will then complete an eligibility questionnaire based on the inclusion and exclusion criteria as laid out above (5.1). Participants must be hemodynamically stable to take part in the study, which will be assessed by the OBGYN provider assessing the patient for their diagnosis.

On day 3 follow up, participants will provide information regarding the time and route they took their misoprostol medication to ensure compliance with the study activities. Patients will be informed in real time regarding their follow up transvaginal ultrasound results at their follow up visits, as they will be able to decide how they want to proceed with management (expectant management, additional medical management with second dose of misoprostol, or surgical management) if ultrasound still confirms the presence of an intrauterine pregnancy. Similarly, any patients who necessitated any additional care as part of their treatment of EPL (e.g. genetic studies on products of conception, infectious disease testing) will have those results shared in the standard manner for all patients seeking care with the Family Planning Division. Participants will report all adverse events (both pregnancy and non-pregnancy related) at each clinical visit.

During the two weeks post-treatment period, if women develop fatigue, malaise, abdominal pain or jaundice, a workup for liver injury should be performed. All patients with elevated LFTs (ALT, AST or total bilirubin) will be followed until resolution. For patients whose LFTs have not returned to normal within

one month, these patients will be referred to a specialist (e.g. hepatologist) for further workup and treatment if necessary.

The study sponsor will evaluate the first 20 patients for their post-treatment LFTs prior to expanding enrollment to the subsequent 20 patients.

Patients identified to have more severe medical adverse events or side effects will be advised to contact the UNC Family Planning Division. Based on the symptomatology and severity, patients will be instructed to seek care through the emergency department/urgent care or through the Family Planning Clinic. All medical adverse events or side effects will be managed based on the standard of care.

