9.4 STATISTICAL ANALYSES

9.4.1 GENERAL APPROACH

Continuous variables will be summarized using mean and standard deviation or median and range depending on the distribution and categorical variables will be described as frequency and percentage. All statistics will be reported with 95% confidence intervals. Where applicable, missing data will be reported as an individual category. As this is a pilot feasibility study with a small sample size, no formal statistical testing will be completed. The principal investigator will be responsible for all data management and data analysis. Statistical calculations will be performed in Stata 15.1.

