10.1.7 CLINICAL MONITORING

Clinical site monitoring is conducted to ensure that the rights and well-being of trial participants are protected, that the reported trial data are accurate, complete, and verifiable, and that the conduct of the trial is in compliance with the currently approved protocol/amendment(s), with International Conference on Harmonisation Good Clinical Practice (ICH GCP), and with applicable regulatory requirement(s).

On-site monitoring will occur for initial assessment and training of sites prior to study participant enrollment. The principal investigator will provide an overview of study activities and participant eligibility criteria to all OBGYN clinical staff at UNC Chapel Hill during a weekly departmental meeting. The principal investigator will also provide an overview of study activities to all key clinical staff members who may come in contact with study participants at the sites for patient recruitment as well as at UNC Chapel Hill Family Planning Clinic where follow up visits will take place. Targeted data verification will be performed by the principal investigator for the first 10 participants approached for recruitment to the study (approximately 10%) to ensure appropriate data collection from the research coordinator. As possible, most transvaginal ultrasounds will be performed by the principal investigator to ensure consistency between imaging findings. Of those not performed by the principal investigator, 20% will be randomly reviewed.

Independent audits will not be conducted.

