10.1.9 DATA HANDLING AND RECORD KEEPING

10.1.9.1 DATA COLLECTION AND MANAGEMENT RESPONSIBILITIES

Data collection is the responsibility of the research personnel at the site under the supervision of the principal investigator. The investigator is responsible for ensuring the accuracy, completeness, legibility, and timeliness of the data reported.

All source documents will be completed via paper and pencil and then transcribed into an electronic 21 CFR Part 11-compliant database to ensure accurate interpretation of data. All patient questionnaires will require an answer to each question with an option to select "Prefer not to answer" to improve data completeness. "Prefer not to answer" will be coded as "99" to denote this value during data analysis. All provider questionnaires will be filled out by consistent study staff, with enrollment visits completed by the study coordinator and all follow up visits completed by the principal investigator.

A data "codebook" will be created for each question of the source documents to ensure that all data is being entered into the electronic database in the same way.

Clinical data (including adverse events (AEs), concomitant medications, and expected adverse reactions data) and clinical laboratory data will be entered into the same 21 CFR Part 11-compliant data capture system provided by UNC. Any missing data from the clinical data abstracted from the EPIC chart will be denoted as "Missing" and will be coded as "98" to denote this value during data analysis. Any missing data will be reviewed in the EPIC chart by the principal investigator to ensure that this data value is not present.

The data system includes password protection and internal quality checks, such as automatic range checks, to identify data that appear inconsistent, incomplete, or inaccurate. Clinical data will be entered directly from the source documents.

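### The principal investigator, who also performs most follow-up scans and does the analysis, asks the acceptability items by telephone; having the coordinator ask them first would reduce possible courtesy bias at little cost.

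*Combined protocol and SAP*

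**What the plan says.** Acceptability is collected once, at the Day 30 telephone contact. Section 4.1, Visit 4: "Participant will be called by the principal investigator to administer a follow up questionnaire". Section 8.1 confirms the content of the call: "All patients will receive a phone call 30 days following misoprostol administration to assess for additional treatments needed, side effects, adverse events, and patient acceptability".

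On the caller's other roles:

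- **Scanning.** Section 4.1, Visit 2: "Participant has a transvaginal ultrasound completed by the principal investigator to ensure that the pregnancy has passed"; Visit 3 is worded in the same way. Section 10.1.7 is weaker: "As possible, most transvaginal ultrasounds will be performed by the principal investigator to ensure consistency between imaging findings". Section 8.1 is more open: "Transvaginal ultrasound will be performed by an obstetrician/gynecologist (fellow or attending) in the UNC Family Planning Clinic".
- **Analysis.** Section 9.4.1: "The principal investigator will be responsible for all data management and data analysis".

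Section 9.4.3 lists four Likert items, to be reported as medians and counts. Two ask whether she would take the regimen again and whether she would recommend it to a friend. The other two ask whether taking the first drug at home, or at another time, would make reuse more or less likely. The objectives table in Section 3 defines acceptability by the first two only.

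Section 4.2 states that there is no comparison group. Sections 4.1 and 9.1 describe the secondary aims as hypothesis-generating.

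**The concern.** The two evaluative items ask a woman to judge a treatment, aloud, for the person running the study, who may also have scanned her. Some respondents soften unfavourable answers in that setting. The protocol describes no neutral interviewer, script or self-completed form for these items. The related provision in Section 10.1.9.1, an option to decline to answer, serves data completeness and does not address courtesy bias.

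In a controlled trial a shift of this kind might affect both arms and largely cancel. Here there is one arm, so it would pass directly into the reported counts. Acceptability is one of three secondary objectives and is part of what the pilot would pass on to a larger trial.

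**Working it through.** The plan states no figure on this point, so there is none to reproduce. The check is a tracing of roles, followed by an illustration of scale.

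**Step 1. Roles**

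| Role | Who | Section |
|---|---|---|
| Asks acceptability, Day 30 | Principal investigator, by telephone | 4.1 (Visit 4) |
| Follow-up scans | Principal investigator (4.1); most, where possible (10.1.7); any fellow or attending (8.1) | as shown |
| Offers further management if the sac remains | Not named | 4.1, 8.2 |
| Analysis | Principal investigator | 9.4.1 |
| Screens participants | Study coordinator | 4.1 (Visit 1) |
| Dispenses UPA | Study coordinators | 6.2.1 |

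Read together, the three statements on scanning support 'most scans' and no more. On advice, Section 8.2 says "Patients will be informed in real time regarding their follow up transvaginal ultrasound results at their follow up visits" but does not say by whom.

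Section 10.1.9.1 has "all follow up visits completed by the principal investigator", but that sentence is about provider questionnaires. Acceptability is a patient questionnaire, so the sentence adds nothing on who asks it. Section 4.1 settles that.

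**Step 2. Scale (illustration only)**

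Let p be the true favourable share and s the share of unfavourable respondents who answer favourably to the caller. The documents give neither, so both are assumptions.

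Observed share = p + s(1 − p). Shift = s(1 − p). Extra favourable answers among the planned 40 = 40 × s(1 − p).

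| p | s | Observed | Shift (points) | Extra of 40 |
|---|---|---|---|---|
| 60% | 10% | 0.60 + 0.10 × 0.40 = 64% | 4 | 1.6 |
| 60% | 25% | 70% | 10 | 4 |
| 60% | 50% | 80% | 20 | 8 |
| 70% | 10% | 0.70 + 0.10 × 0.30 = 73% | 3 | 1.2 |
| 70% | 25% | 77.5% | 7.5 | 3 |
| 70% | 50% | 85% | 15 | 6 |
| 80% | 10% | 0.80 + 0.10 × 0.20 = 82% | 2 | 0.8 |
| 80% | 25% | 85% | 5 | 2 |
| 80% | 50% | 90% | 10 | 4 |

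The range is 2 to 20 points, or about 1 to 8 women.

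**Step 3. Comparison with sampling error**

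Exact (Clopper-Pearson) 95% intervals at n = 40:

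- 24/40: 43.3% to 75.1%, half-width (75.1 − 43.3)/2 = 15.9 points
- 28/40: 53.5% to 83.4%, half-width (83.4 − 53.5)/2 = 15.0 points
- 32/40: 64.4% to 90.9%, half-width (90.9 − 64.4)/2 = 13.3 points

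In seven of the nine rows the shift is smaller than the half-width. It reaches or passes it only at s = 50% with p at 60% or 70%. The two quantities differ in kind, however. An interval describes sampling error around whatever is being measured. If the true share is 70% and 85% is observed, the interval is that for 34/40, 70.2% to 94.3%, which lies wholly above the truth. More participants would narrow the interval without moving it back.

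**The case against.** The case for leaving Visit 4 alone has real substance.

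- **Nothing here is contradictory or uncomputable, and nothing is decided on it.** Acceptability is secondary, has no threshold and is not tested. The feasibility criteria in Section 9.1 are recruitment, adherence and retention. This stands, and it limits the point to an inexpensive improvement.
- **The size is assumed.** This also stands. The documents contain no information on p or s, and the planned output is medians and counts, not a percentage favourable.
- **Not every item invites approval.** The questions about place and timing of the first drug have no obviously pleasing answer. The concern is confined to the other two.
- **The coordinator is not neutral either.** The coordinator screens women, offers them admission to the study and dispenses the drug they are asked to judge. So the change can be expected to reduce the bias, not to avoid it. It still separates the question from the study lead and usual sonographer.
- **Self-completion has a cost.** The forms filled in by participants at Visits 2 and 3 are completed in clinic, whereas Day 30 is a call. A woman whose sac is absent at Visit 2 has no later clinic visit, so a remote form would be needed, with some non-return among 40 women. That favours the coordinator as the main route.

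A reader might also infer that the principal investigator advises every woman on further treatment. The documents do not support this: no adviser is named, the offer reaches only women with a retained sac, and initial counselling comes from the clinical team before research staff approach (Section 5.5). Nor does the analysis role itself make answers more favourable. It means only that the person who asks also tabulates.

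**Conclusion.** The point holds in a limited form. The principal investigator asks the acceptability items by telephone, performs most follow-up scans and does all the analysis. In a single-arm study, courtesy bias in the two evaluative items would be invisible in the results and would not cancel.

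The size is unknown. The range of 2 to 20 points rests on an assumed true share of 60% to 80% and an assumed 10% to 50% of unfavourable respondents changing their answer. A reader might conclude that the acceptability results will be inflated, or that they cannot be used. The documents support neither: they show an arrangement open to bias, not bias itself. The primary feasibility outcomes are not affected.

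**What to change.** Amend Section 4.1, Visit 4, and the matching text in Section 8.1:

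1. The study coordinator asks the four acceptability items at the start of the Day 30 contact, before any clinical questions. Moving all four keeps the questionnaire together, although only two are at issue.
2. The principal investigator then asks about additional treatment, side effects and adverse events, as now planned.
3. Alternatively, the participant completes the acceptability items herself, with a coordinator call if the form is not returned.
4. The report states who asked the items and by what mode.

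The cost is a few minutes of existing coordinator time and slightly more coordination of one contact, with no new staff. The self-completed route also needs a short form in English and Spanish and carries some risk of non-return. Either route would reduce the bias; neither can be assumed to remove it.
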